1.2 Secondary Objectives

- To determine the safety and feasibility of hCG supplementation with Pregnyl® in combination with standard immunosuppressive therapy in pediatric and adult patients with high-risk or refractory aGVHD
- To determine the incidence of acute GVHD flare after CR/PR requiring increase of steroids or other systemic treatment at days 28 and 56
- To compare the rate of treatment failure for acute GVHD at days 28 and 56 after initiation of protocol therapy to historical controls

1.3 Correlative Objectives

- Pharmacokinetics (clearance, half-life, volume of distribution) of the both the hCG and EGF components of urinary hCG when administered to patients with GVHD
- Monitoring for hormonal effects via determination of serum concentrations of hCG, estradiol, progesterone, and testosterone on days 7, 14, 28, and 56, compared to baseline
- Collection of blood samples for measurement of immune and tissue damage/repair biomarkers to determine change from pre-treatment levels to levels obtained on days 7, 14, 28, and 56 post-treatment
- Analysis of previously collected skin and/or gastrointestinal biopsies for biomarkers of refractory aGVHD and response to therapy

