addition to providing mitogenic signals for intestinal epithelial stem cells, EGF also has been shown to regulate inflammation, intestinal epithelial apoptosis, and autophagy in the setting of necrotizing enterocolitis [11]. Chronic administration of intraluminal EGF enhanced colonic mucosal growth in both a rodent model [12] and in humans [13]. However, intraluminal administration is not practical or likely to be efficacious in steroid-refractory aGVHD due to the typical widespread gastrointestinal involvement. Feasibility of *systemic* treatment with EGF has recently been demonstrated. In a randomized, placebo-controlled trial of intravenous recombinant EGF in premature infants with necrotizing enterocolitis, 6-day continuous IV administration of EGF at 100 ng/kg/hour improved gut mucosal thickness by 54% over baseline as early as day 4 of therapy [14]. No significant infusional or other systemic side effects from EGF administration were noted in the trial. Whether similar responses could be elicited in steroid-refractory aGVHD has not been tested. Unfortunately, pharmaceutical grade recombinant EGF is not currently available for clinical testing in humans, making alternate sources of EGF necessary.

Circulating EGF levels are high and excreted in the urine during pregnancy.

In recent studies of the immune and growth factor milieu of early pregnancy, EGF levels have been identified as being approximately 20-fold elevated in the first trimester of pregnancy, while several inflammatory biomarkers were significantly decreased ([Table 1](#)) relative to non-pregnant controls ([name] et al, manuscript accepted). EGF is critical for the initiation and maintenance of pregnancy by stimulating hCG production in the early developing placenta [15]. As pregnancy progresses, deficiency of EGF leads to intrauterine growth retardation [16] and can predispose to necrotizing enterocolitis [17]. Considering its importance in placentation and fetal growth, it is not a surprise that EGF is a biologically functional component of commercial urinary-derived hCG preparations. With testing by the Cytokine Reference Laboratory at the University of Minnesota, the concentration of EGF in Pregnyl® was determined to be 7,037 pg/mL ([name], unpublished data).

Analyte	Non-pregnant Median (N=11)	Min	Max	Pregnant Median (N=16)	Min	Max	p
EGF	24.8	8.6	178.2	489.4	14.6	1506	0.003
sCD40L	424.7	132.7	1423	29.2	0	1583	0.004
L-17	14.8	2.2	161.6	5.5	<LLD	46.9	0.03

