Urinary HCG is an inexpensive, commercially-available hormone with a long track record of safety and tolerability. Therefore, if effective, we anticipate this could quickly be repurposed into a standard adjunctive treatment for high-risk or refractory aGVHD.

The first goal of this study is to find the dose of Pregnyl® needed to at least double patients' plasma EGF levels from baseline levels while not exceeding the maximum tolerated dose. Our preliminary data indicate that baseline plasma EGF levels are in the range of 10-30 pg/ml, whereas the median plasma EGF level of a normal allogeneic HCT recipient without aGVHD is over 10-fold higher at 140 pg/mL.

Dose justification: The doses selected for testing in this trial are within the range of doses of Pregnyl® used for endocrinology purposes today and do not represent "high" doses. The standard dose for ovulation trigger is 10,000 USP of the hCG component, which is more than double the amount that patients on the highest dose level on this protocol will receive. The starting doses for this protocol are estimated to be the minimum sufficient to determine an increase in plasma EGF with therapy. The 1-week cumulative EGF dose obtained from Pregnyl® at dose level 1 is expected to be equivalent to approximately 50% of the circulating EGF in a typical patient with severe aGVHD. The 1-week cumulative EGF dose at dose level 2 is expected to be

approximately 100% of (effectively doubling) circulating EGF in patients with severe aGVHD. Each lot of Pregnyl® will be tested for EGF content prior to administration so that the precise EGF dose administered is known.

4 Study Design

This multi-center phase I/II study will use Continual Reassessment Method (CRM) to establish a maximum tolerated dose (MTD) of human chorionic gonadotropin and epidermal growth factor supplementation (hCG) as an adjunct to facilitate improved mucosal healing and immune tolerance in conjunction with accepted, standard immunosuppressive therapy in the setting of high-risk (Arm 1), steroid dependent (Arm 2A), and steroid-refractory (Arm 2B) acute graft-versus-host disease (aGVHD).

Enrollment and dose escalation of Pregnyl® will be independent for each arm.

Arm 1, Phase I: For each arm up to 5 dose levels of Pregnyl® will be tested; however dose levels -1 and -2 will be used only if dose level 1 proves too toxic. In addition to Pregnyl®, patients will continue on their current standard of care aGVHD treatment.

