7.3 Arm 2B – Steroid-Refractory aGVHD

Standard of care immunosuppression, plus Pregnyl® (hCG supplementation) at assigned dose subcutaneously every other day for 7 doses.

If a patient has a toxicity that fits the definition of dose limiting as defined in the phase I section below, the patient will discontinue study treatment.

Continue protocol treatment through day 14. Assess response at day 14:

- **If a complete or partial response**, the patient is eligible to receive Pregnyl maintenance at the same dose twice weekly for 10 doses beginning day 15 to 17. Refer to [section 9](#) for response definitions.
- **If no response**, the patient will be taken off study treatment

Pregnyl® dose level assignment will be done by treatment arm, with Arm 2 independent of Arm 1.

For phase I, up to 7 dose levels of Pregnyl® will be tested; however dose levels -1 and -2 will be used only if dose level 1 proves too toxic. The reason for this expansion is lack of rise in plasma EGF levels with Pregnyl therapy in patients with the most severe aGVHD in the first 6 patients in phase 1.

Dose Level	Dose
-2	125 USP hCG/875 pg EGF/m ²
-1	250 USP hCG/1,750 pg EGF/m ²
1 (start)	500 USP hCG/3,500 pg EGF/m ²
2	1,000 USP hCG/7,000 pg EGF/m ²
3	2,000 USP hCG/14,000 pg EGF/m ²
4	3,500 USP hCG/24,500 pg EGF/m ²
5*	5,000 USP hCG/35,000 pg EGF/m ²

***NOTE: To avoid using vials from more than one Lot of study product, the maximum dose is either (1) the contents of a single 10,000 IU vial, or (2) a maximum dose of 10,000 IU from multiple vials. All vials used should be from the same Lot.**

The 1st 2 patients will be enrolled in dose level 1. The next cohort of 2 patients will not begin treatment until all patients in the current cohort has reached day 21 to assess for dose limiting toxicity (DLT).

DLT is defined as any of the following occurring by day 21 after the 1st dose of Pregnyl® (phase I component only):

- In males and females: Grade 2-4 thromboembolic event (CTCAE v4) i.e., any thrombosis more severe than a superficial venous thrombosis develops and treatment with anticoagulation is required
- In males and females: Grade 3-4 ascites (CTCAE v4)
- Specific to females: Grade 3-4 ovarian hyperstimulation syndrome, defined as the rapid development of enlarged, cystic, painful ovaries—refer to [section 11.2](#) for CTCAE grading guidance

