- **Progression:** deterioration of any organ involved.

- **No Response (NR):** absence of any improvement or progression as defined above.

10 Schedule of Patient Activities

Scheduled evaluations after screening and through day 19 of the last treatment cycle may be performed +/-2 days from the targeted date; assessments performed after day 28 and through day 56 may be done +/-5 days of the targeted date. After day 56, assessments will coincide with the post-transplant follow-up schedule (i.e., additional clinic visits specifically for this study will not be required). In addition, targeted days may be altered as clinically appropriate, and will not constitute a protocol deviation.

Schedule of Treatment, Tests and Procedures – Arm 1

	Baseline	Treatment Days +/- 2 days												Phase I only	Follow Up +/- 5 days***	
Procedures, evaluations, and treatment		1	3	5	7	9	11	13	14	15	17	19		21	28	56
Standard of Care																
Vital signs and weight	X	X	X	X	X	X	X	X	X	X	X	X			X	X
Performance status (Karnofsky or Lansky)	X				X				X			X			X	X
Acute GVHD staging	X				X				X						X	X
Complete blood count	X				X				X			X			X	X
Complete metabolic panel	X				X				X			X			X	X
Serum creatinine	X															
Ejection Fraction by echocardiogram or MUGA	X															
Research																
Pregnyl® dosing*		X	X	X	X	*										
Assess for toxicity		beginning with the 1st dose of Pregnyl® and continuing for 4 weeks after the last dose per section 11.2 (if phase I assess for DLT at day 21)														
Pharmacokinetics**		X			X											
Serum hCG	X^				X				X						X	X
Estradiol, progesterone, and testosterone	X				X				X						X	X
Collection of blood samples for immune and tissue damage/repair biomarkers (refer to section 10.3 for blood volume and tube type)s	X				X				X						X	X

MT2014-12: hCG supplementation in high-risk or refractory aGVHD

Research related blood samples will go to Translational Therapy Lab (TTL) for processing and storage until study related testing.

*If a patient achieves a complete or partial response, he/she may continue to receive maintenance Pregnyl® doses twice per week, in the dose level he or she was already assigned, for another 10 doses, beginning during protocol day 9-12.

**Blood samples (2 ml plasma) collected 30 (\pm 10) minutes pre-dose, and at post-dose 1 hour (\pm 5 min), 3 hours (\pm 5 min), 6 hours (\pm 10 min), and 24 hours (\pm 30 min).

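### Correlative EGF, hCG, sex-hormone and biomarker draws on days 7, 14 and 28 have no time-since-dose rule, so summaries by nominal day mix peak, trough and off-drug values

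*Combined protocol and SAP*

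**What the plan says.** - **Sampling days.** Sections 1.3 and 10.1 place the correlative draws at baseline and days 7, 14, 28 and 56. The biomarker draws serve "to determine change from pre-treatment levels to levels obtained on days 7, 14, 28, and 56 post-treatment". Plasma EGF belongs to this panel (section 10.1, item 4). hCG, estradiol, progesterone and testosterone follow the same days. No pre-dose or post-dose time is set for any of them.
- **Windows.** Section 10 allows 2 days either side through day 19. Later, "assessments performed after day 28 and through day 56 may be done +/-5 days of the targeted date", and the schedule tables put day 28 under the same 5-day heading. Days may also be moved for clinical reasons without counting as a deviation.
- **Dosing.** Induction is every other day: days 1 to 7 in Arm 1 and days 1 to 13 in Arms 2A and 2B. Responders may then receive ten twice-weekly doses, starting on day 9 to 12 (Arm 1) or day 15 to 17 (Arm 2).
- **Timed samples.** Only the PK series has clock times: 30 minutes pre-dose, then 1, 3, 6 and 24 h post-dose. It measures EGF and hCG on days 1 and 7 in Arm 1, and on day 1 and once more near the end of induction in Arm 2.
- **Use of EGF levels.** Section 3 states: "The first goal of this study is to find the dose of Pregnyl® needed to at least double" plasma EGF. Section 7.3 says of the two added Arm 2B levels: "The reason for this expansion is lack of rise in plasma EGF levels with Pregnyl therapy".
- **Analysis.** Section 13.3 summarises correlative measures by arm and time point, with no term for time since dose.

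**The concern.** A drug level has meaning only relative to the dose before it. Day 7 is a dosing day in every arm, so a day 7 draw may come 48 h after dose 3 or an hour after dose 4, and both count as day 7. At days 14 and 28, patients on maintenance are pooled with non-responders who have stopped treatment. Because response decides who continues dosing, the exposure-response correlations in section 10.1 are also affected: a higher level in responders may show only that they were still being dosed.

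The EGF readings have already influenced the design, since they are the stated reason for extending the Arm 2B dose range. Section 3 sets a doubling goal but names no sample, time point or analysis for judging it.

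**Working it through.** **1. Windows against dosing intervals**
- Early window: 2 days either side spans 4 days, against a 2-day dosing interval.
- Late window: 5 days either side spans 10 days, against 7/2 = 3.5 days.
- Nominal time since last dose at day 14: 1 day in Arm 2 (last dose day 13); 0 to about 3 days in Arm 1 patients on maintenance; 14 − 7 = 7 days in Arm 1 non-responders.
- Nominal time at day 28 in non-responders: 28 − 7 = 21 days (Arm 1) or 28 − 13 = 15 days (Arm 2). Patients on maintenance may be anywhere in the 3.5-day cycle.
- Day 56: the last maintenance dose falls at start + 9 × 3.5 = start + 31.5 days, so day 40.5 to 43.5 (Arm 1) or 46.5 to 48.5 (Arm 2). The window opens on day 51. Dosing is over, so the issue at day 56 is washout.

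**2. The plan's own dose figures**
- Section 2 reports that "the concentration of EGF in Pregnyl® was determined to be 7,037 pg/mL". At 10,000 USP in 10 mL this is 7,037 × 10 / 10,000 = 7.037 pg per USP, or 3,518 pg per 500 USP. The level 1 label of 3,500 pg reproduces.
- Section 3: "The 1-week cumulative EGF dose obtained from Pregnyl® at dose level 1 is expected to be equivalent to approximately 50% of the circulating EGF". For level 2 it gives "approximately 100% of (effectively doubling) circulating EGF in patients with severe aGVHD". Section 3 also states "baseline plasma EGF levels are in the range of 10-30 pg/ml".
- Weekly share at level 1 = 4 doses × 3,500 pg/m² × body surface area / (plasma volume × baseline EGF). Assuming 1.8 m², 3 L and 17 pg/mL: 25,200 / 51,000 = 49%. Over 2.5 to 5 L and 10 to 30 pg/mL it runs from 101% (25,200 / 25,000) down to 17% (25,200 / 150,000). The plan's 50% is attainable, but its own inputs do not fix it.

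**3. Drug-derived concentration, 6 h against 48 h after a dose**

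Ratio = 2^(42/h), with half-life h assumed:
- 12 h: 11.3
- 24 h: 3.4
- 36 h: 2.2

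This applies to hCG as far as endogenous hCG is low, and to the drug-derived part of EGF only.

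**4. Total EGF**

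Model: one compartment, instantaneous absorption, constant endogenous baseline, doses at 0, 48, 96 and 144 h. Fold over baseline = 1 + a × Σ 2^(−time since each dose / h). The per-dose increment a is the plan's weekly share divided by 4 (50% / 4 = 12.5% at level 1), scaled by dose. Half-life varies from 72 h down to 1 h. The swing compares just after the day 7 dose with 48 h later; at short half-lives it tends to 1 + a.

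| Level | a | Swing, 72 h to 1 h half-life |
|---|---|---|
| 1 | 0.125 | 1.09 to 1.125 |
| 2 | 0.25 | 1.16 to 1.25 |
| 3 | 0.50 | 1.25 to 1.50 |
| 4 (Arm 2B) | 0.875 | 1.33 to 1.875 |
| 5 (Arm 2B) | 1.25 | 1.38 to 2.25 |

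At level 5 the swing is 2.15 at a 12 h half-life and 1.88 at 24 h. If the weekly share at level 1 were 101% instead of 50%, a at level 3 would be 4 × 1.01 / 4 = 1.01, and the short-half-life swing about 2.0.

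**5. Missing a real doubling**

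If EGF is exactly two-fold at peak, the reading 48 h later is 1 + 0.5^(48/h): 1.00 at 6 h, 1.06 at 12 h, 1.25 at 24 h, 1.40 at 36 h and 1.63 at 72 h.

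**6. Would pre-dose draws show the rise?**

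Not at short half-lives. For 12 h or less, the pre-dose fold on day 7 is at most 1.03 at level 3 and 1.08 at level 5. Pre-dose sampling makes values comparable, but it cannot test doubling.

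**The case against.** The strongest reply is that timed data already exist. On day 7 in Arm 1, and once late in induction in Arm 2, EGF and hCG are measured at known times, and these samples could answer the doubling question. That stands, and the fix uses it. But the documents never link the PK series to the doubling goal, and the series covers neither sex hormones, nor day 28, nor day 14 in Arm 1.

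The stakes are also limited. Doubling is a goal in the rationale, not a listed objective or endpoint. The MTD rests on DLTs. The blood biomarker work is labelled exploratory and its planned analysis is descriptive. All of that stands.

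Three stronger readings are tempting, and the documents support none of them:
- **Timing swamps a two-fold rise in general.** The 11-, 3.4- and 2.2-fold ratios concern the drug-derived part only. On the plan's own increments, total EGF shifts at most 1.5-fold at levels 1 to 3. A two-fold shift needs level 5 with a half-life of about 12 h or less, or a larger dose share than section 3 expects.
- **The Arm 2B extension followed from late draws.** Sections 7.3 and 13.2 do not say which samples, or which times, showed no rise.
- **No analysis could repair the data.** If dose and draw times are captured, time since dose can be modelled. The case report forms are not among the documents, so failure to capture it is not shown.

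**Conclusion.** The concern holds for the correlative draws on days 7, 14 and 28. They lack a time-since-dose rule, their windows exceed the dosing interval, and the planned summary treats unlike samples as alike. Any distortion of EGF can run either way: depending on the half-life, a real doubling may be missed or a brief peak taken for a sustained one.

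The sizes rest on assumed half-lives and a simple one-compartment model. The total-EGF figures also take section 3's 50% and 100% shares at face value. No size can be given for sex hormones or the other biomarkers. Day 56 samples are taken after dosing ends and need labelling, not a pre-dose rule. The point is worth acting on because plasma EGF has already influenced a dose-range decision and the remedy is cheap. It does not touch the DLT-based MTD or the phase II response endpoint.

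**What to change.** 1. **Section 10 schedules, as a footnote:** draw the day 7 correlative samples before that day's dose. For patients on maintenance, draw the day 14 (Arm 1) and day 28 samples before a scheduled dose within the window. The draw moves; the dosing schedule does not.
2. **Case report form:** record hours since the last dose for every correlative draw, including day 14 in Arm 2, day 56 and all draws in non-responders.
3. **Section 13.3:** summarise off-drug samples (non-responders after stopping, and day 56) separately from on-treatment samples.
4. **Section 3 or 10.1:** state that the EGF-doubling goal is judged on the baseline-corrected PK samples at 1, 3, 6 and 24 h, not on pre-dose or untimed draws.

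Cost: slightly less flexible draw timing, one form field and a few lines of text. No extra blood or visits.

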1.4 Transplant Related Objectives

- To determine the disease-free survival, overall survival, and non-relapse mortality at day 28, 56, 180 and 1 year of protocol treatment
- To determine the incidence of chronic GVHD at day 180 and 1 year

2 Background

Patients with high-risk acute graft-versus host disease (HR-aGVHD) have poor responses to initial therapy and an increased risk of death.

In the US, nearly 7,000 patients undergo allogeneic hematopoietic cell transplantation (HCT) annually in an effort to cure hematologic malignancies and other bone marrow disorders. The majority of allogeneic HCT recipients will experience acute graft-versus-host disease (aGVHD), a complication in which cells from the immunocompetent donor graft attack the recipient's organs and tissues [1]. Patients with severe skin or visceral involvement, or multi-organ aGVHD, have high-risk disease, characterized by a less than 50% complete or partial response to first-line, high-dose corticosteroids and a 2-3 fold risk of treatment-related mortality [2]. Before the recent ability to discriminate high-risk versus standard-risk aGVHD based upon organ staging at onset, it was noted that one-half of patients aGVHD did not sustain response to first-line therapy with corticosteroids (i.e., are *steroid-refractory*) [3]. Damage to the gastrointestinal tract is the major cause of morbidity and mortality in patients with severe, refractory aGVHD.

Figure 1 shows typical colonoscopic findings of a University of Minnesota patient with aGVHD with mucosal edema, erythema, loss of normal vascular patterns, and extensive ulcerations. Clinically, such patients have anorexia, abdominal cramping and pain, malabsorption, and large volume (often >2 liters) of diarrhea daily. They become severely malnourished, require intravenous medications and nutrition due to poor oral absorption, and they consequently endure very prolonged hospital stays. 80-100% of patients die within two years of the development of steroid-refractory [4] (and unpublished quality improvement data).

Figure 1. Appearance of transverse colon in a patient suffering from steroid-refractory aGVHD.

Current standard treatment of aGVHD depletes circulating and tissue immune effector cells. The reason for poor outcomes in high-risk and steroid-refractory aGVHD is likely *not solely* due to poor efficacy of immunosuppressant medications. High-dose steroids, calcineurin inhibitors, anti-thymocyte globulin, and anti-cytokine therapies effectively deplete the circulating pool of cytokine-producing cells

responsible for GVHD effects. **Figure 2**

[figure not shown]

Figure 2. Spectrum of TNF α -producing and non-TNF α -producing peripheral blood leukocytes after stimulation with lipopolysaccharide in a normal donor (left) versus a patient treated for steroid-refractory aGVHD (right).

It is apparent that TNF α -producing monocytes and lymphocytes, the cell subsets responsible for aGVHD effects, are substantially depleted from the peripheral blood of the steroid-refractory aGVHD patient.

These inflammatory cytokine-producing cells are also depleted from colonic tissue in patients with refractory aGVHD. **Figure 3** shows that the lamina propria in a patient with refractory aGVHD (right) is relatively devoid of hematopoietic cells (CD45 staining in brown) compared to that of a normal donor (left, [name], unpublished data). Based upon these preliminary findings as well as >20 years of intensified

[figure not shown]

Figure 3. Fewer CD45+ (brown) hematopoietic cells in colon tissue (lamina propria) normal donor (left) versus a patient treated for steroid-refractory aGVHD (right).

immunosuppression as the sole paradigm for high-risk or refractory aGVHD, it is very unlikely that investigational drugs that exert their effects by intensification of immune suppression will be able to facilitate healing or improve organ function. New paradigms aimed at supporting immunologic tolerance as well as restitution of damaged tissues such as the methods proposed in this trial are necessary.

Mucosal healing capacity may be reduced in high-risk or refractory GVHD due to deficiency of trophic growth factors.

Markers of endothelial damage (angiopoietin-2) and angiogenesis (vascular endothelial growth factor, VEGF) have been shown to be prognostic in steroid-refractory acute GVHD [5]. A recent broader study of angiogenic factors in allogeneic HCT has been completed. In that pilot study, epidermal growth factor (EGF) levels were over 10-fold lower in 17 patients experiencing severe (grade III or IV) aGVHD compared to 17 allogeneic HCT recipients at 3-months post-HCT who did not experience aGVHD (median 11.5 vs 141.4 pg/ml, p=0.004). The finding of low EGF levels at the onset of aGVHD was subsequently validated in two independent cohorts of patients enrolled on multicenter treatment trials, Blood and Marrow Transplant Clinical Trials Network (BMT CTN) 0302 and 0802 compared to a separate cohort of patients without aGVHD [[6], and [name] et al, manuscript accepted]. Furthermore, in BMT CTN 0802, where plasma (as opposed to serum, which can have EGF levels increase due to release from activated platelets) was analyzed, EGF levels significantly *decreased* at day 28 after initial aGVHD therapy (p=0.01, Wilcoxon signed rank) in patients who had no response. This was particularly apparent in patients who had high-risk aGVHD at onset (**Figure 4, top**), where day 28 median EGF was 6-fold lower (3.8 versus 23.2 pg/mL) in patients with no response to initial therapy. In contrast, patients with complete responses to initial therapy demonstrated *increases* in plasma EGF by day 28 of treatment.

[figure not shown]

Figure 4. Plasma EGF levels at aGVHD onset and day 28 of initial therapy in patients enrolled in BMT CTN 0802, stratified by high-risk aGVHD and standard risk aGVHD. Patients with high-risk (top) and standard risk aGVHD (bottom) and no response (NR) to therapy show a decline in EGF levels at day 28 of therapy, with the decrease even more dramatic in high-risk aGVHD.

Decreased circulating EGF levels have been identified in inflammatory bowel disease [7], which shares many manifestations with GVHD. EGF has been shown to enhance gut epithelial restitution after radiation injury [8] and protect against the development of colitis in a rat model [9]. Furthermore, EGF treatment can improve ion transport capabilities, especially sodium reabsorption, in inflamed colonic mucosa [10]. In

addition to providing mitogenic signals for intestinal epithelial stem cells, EGF also has been shown to regulate inflammation, intestinal epithelial apoptosis, and autophagy in the setting of necrotizing enterocolitis [11]. Chronic administration of intraluminal EGF enhanced colonic mucosal growth in both a rodent model [12] and in humans [13]. However, intraluminal administration is not practical or likely to be efficacious in steroid-refractory aGVHD due to the typical widespread gastrointestinal involvement. Feasibility of *systemic* treatment with EGF has recently been demonstrated. In a randomized, placebo-controlled trial of intravenous recombinant EGF in premature infants with necrotizing enterocolitis, 6-day continuous IV administration of EGF at 100 ng/kg/hour improved gut mucosal thickness by 54% over baseline as early as day 4 of therapy [14]. No significant infusional or other systemic side effects from EGF administration were noted in the trial. Whether similar responses could be elicited in steroid-refractory aGVHD has not been tested. Unfortunately, pharmaceutical grade recombinant EGF is not currently available for clinical testing in humans, making alternate sources of EGF necessary.

Circulating EGF levels are high and excreted in the urine during pregnancy.

In recent studies of the immune and growth factor milieu of early pregnancy, EGF levels have been identified as being approximately 20-fold elevated in the first trimester of pregnancy, while several inflammatory biomarkers were significantly decreased ([Table 1](#)) relative to non-pregnant controls ([name] et al, manuscript accepted). EGF is critical for the initiation and maintenance of pregnancy by stimulating hCG production in the early developing placenta [15]. As pregnancy progresses, deficiency of EGF leads to intrauterine growth retardation [16] and can predispose to necrotizing enterocolitis [17]. Considering its importance in placentation and fetal growth, it is not a surprise that EGF is a biologically functional component of commercial urinary-derived hCG preparations. With testing by the Cytokine Reference Laboratory at the University of Minnesota, the concentration of EGF in Pregnyl® was determined to be 7,037 pg/mL ([name], unpublished data).

Analyte	Non-pregnant Median (N=11)	Min	Max	Pregnant Median (N=16)	Min	Max	p
EGF	24.8	8.6	178.2	489.4	14.6	1506	0.003
sCD40L	424.7	132.7	1423	29.2	0	1583	0.004
L-17	14.8	2.2	161.6	5.5	<LLD	46.9	0.03
IL-6	7.9	<LLD	82	<LLD	<LLD	34.3	0.03

Table 1. Differences in serum growth factors and markers of inflammation between pregnant (first trimester) and non-pregnant individuals. LLD=lower limit of detection.

Tolerance induction during pregnancy: central role of hCG.

HCG is widely studied for its immune tolerance-inducing effects. Recently described immunomodulatory properties of hCG include stimulating an increase in regulatory T cells with a concomitant reduction of inflammatory cytokines [18], maintenance of dendritic cells in a tolerogenic state [19], and modulation of innate immunity [20]. The molecular mechanisms of hCG-induced immune modulation are not completely known but involve inhibition of nuclear transcription factor- κ B and activator protein-1 gene transcription driven by TNF α [21]. Recently, chronic administration of low-dose hCG was piloted as a therapy for refractory chronic GVHD and found to be tolerable with suggestion of clinical efficacy [22]. In this study, an increase in indoleamine 2,3-dioxygenase (IDO) and IL-10 blood levels were observed, both beneficial for runaway GVHD immune responses. It is possible that some of the results, including the gut epithelial restitution depicted in this report, were also due to supplementation of EGF.

Potential complementary roles of EGF and hCG in high-risk and steroid-refractory aGVHD.

It is possible that both the hCG and EGF components of Pregnyl® will contribute to improvement of clinical outcomes in high-risk and refractory aGVHD. HCG is well known for its ability to induce immunologic tolerance, and EGF is well known for its role in repair of damaged tissues. Considering the gut trophic properties of EGF and the immune modulatory properties of hCG, our **central hypothesis** is that administration of an EGF-containing urinary preparation of hCG to patients with steroid-refractory aGVHD may help restore organ function, support the development of immunologic tolerance, and improve quality of life, and without adding significant toxicity to standard immunosuppressive therapy. Before large scale application of this approach, the safety, feasibility, pharmacokinetic, immunologic and other pharmacodynamic correlates of its administration in a limited number of patients must first be determined.

Subcutaneously-delivered urinary hCG has safely been given to both men and women for endocrinologic indications, with data regarding safety and efficacy spanning over 4 decades [23, 24, 25, 26, 27]. Severe reactions including arterial thromboembolism and ovarian hyperstimulation syndrome occur in <1% of patients. The doses administered on this protocol are within the range of established standard of care dosing for endocrinologic indications today. Similar low doses of urinary hCG given to a cohort of patients with steroid-refractory chronic GVHD was well tolerated. Therefore, we believe the safety risks of this study are very minimal. However, the

doses required to significantly increase plasma and tissue EGF levels and exert immunologic effects are not known, making the studies proposed herein necessary for further repurposing of the drug.

3 Summary and Rationale

High-risk and steroid-refractory acute graft-versus-host disease (aGVHD) are frequent and often fatal complications of allogeneic hematopoietic cell transplantation (HCT). The current treatment paradigm, intensification of immunosuppression, does not yield durable improvement of organ (especially gastrointestinal) function or long-term survival in most patients. Many patients die of consequences of severe mucosal damage of the gastrointestinal tract and complications of profound immunosuppression. This study takes an entirely different approach to the treatment of otherwise fatal aGVHD by hastening mucosal healing and inducing immune tolerance with the hormonal supplement, Pregnyl®. We recently identified that circulating epidermal growth factor (EGF) levels are very low in patients with severe aGVHD compared to allogeneic HCT recipients without aGVHD. EGF is an important protein involved in the proliferation of epidermal and epithelial cells, and it is involved in healing of damaged mucosal tissues. Extensive preclinical and clinical data has demonstrated that administration of EGF induces remission of other life-threatening forms of intestinal inflammation, such as necrotizing enterocolitis and inflammatory bowel disease, but this approach has never been tested in aGVHD. A readily available and inexpensive source of EGF is urinary-derived human chorionic gonadotropin (hCG) (e.g., Pregnyl® and other brands) which is commonly used for reproductive endocrinology indications. Pregnyl® is isolated from the urine of pregnant women which contains both hCG and EGF. Although the EGF component contained in Pregnyl® is not essential for reproductive endocrinology indications, it may be highly effective in providing EGF for repair of tissues damaged by aGVHD.

HCG is a hormone critical for the development of maternal immune tolerance towards a fetus during pregnancy, arguably the most commonly encountered and effective example of induced immune tolerance in nature. HCG induces immune tolerance in pregnancy by mechanisms including induction of indoleamine 2,3 dioxygenase (IDO) and expansion of endogenous regulatory T cells (Tregs), both of which are protective against GVHD. Therefore, hCG may be effective in promoting immune tolerance in aGVHD. Importantly, a urinary-derived preparation of hCG has already shown early promise in inducing tolerance and reversing organ damage without untoward toxicity in 12 of 20 (60%) of patients with heavily pre-treated patients with steroid-refractory or intolerant chronic GVHD [22].

The objective of this study is to test for the first time the use of supplemental EGF and hCG (Pregnyl®) as an adjunct to facilitate improved mucosal healing and immune tolerance in addition to accepted, standard immunosuppressive therapy in the setting of high-risk (Arm 1) and steroid-refractory (Arm 2) aGVHD. Our central hypothesis is that administration of urinary hCG and EGF will provide (a) EGF for facilitation of gastrointestinal healing and (b) hCG for induction of immune tolerance, while not worsening the rates of infectious or other complications, in patients with severe aGVHD. However, the optimal supplemental doses of EGF necessary to achieve an epithelial restitution effect are not known. Therefore, this study will use the Continuous Reassessment Method (CRM) to test up to five dose levels of Pregnyl® in order to identify the maximum tolerated dose (MTD) by each patient cohort (high-risk (arm 1), steroid dependent (arm 2A) and steroid-refractory (arm 2B)). We will determine pharmacokinetics of both the EGF and hCG components of urinary HCG and identify correlative biomarkers of aGVHD response. The pharmacokinetic and correlative studies would not be possible without intercollegiate collaborations. The knowledge gained from these aims will provide critical feasibility, preliminary safety, and correlative data for efficacious dose selection and identification of leading biomarkers for the phase II expansion of this trial. These data will be necessary to successfully compete for National Institutes of Health or similar funding for a larger scale, multicenter trial, if the approach proves to be feasible, tolerable, and efficacious in this initial study.

Urinary HCG is an inexpensive, commercially-available hormone with a long track record of safety and tolerability. Therefore, if effective, we anticipate this could quickly be repurposed into a standard adjunctive treatment for high-risk or refractory aGVHD.

The first goal of this study is to find the dose of Pregnyl® needed to at least double patients' plasma EGF levels from baseline levels while not exceeding the maximum tolerated dose. Our preliminary data indicate that baseline plasma EGF levels are in the range of 10-30 pg/ml, whereas the median plasma EGF level of a normal allogeneic HCT recipient without aGVHD is over 10-fold higher at 140 pg/mL.

Dose justification: The doses selected for testing in this trial are within the range of doses of Pregnyl® used for endocrinology purposes today and do not represent "high" doses. The standard dose for ovulation trigger is 10,000 USP of the hCG component, which is more than double the amount that patients on the highest dose level on this protocol will receive. The starting doses for this protocol are estimated to be the minimum sufficient to determine an increase in plasma EGF with therapy. The 1-week cumulative EGF dose obtained from Pregnyl® at dose level 1 is expected to be equivalent to approximately 50% of the circulating EGF in a typical patient with severe aGVHD. The 1-week cumulative EGF dose at dose level 2 is expected to be

approximately 100% of (effectively doubling) circulating EGF in patients with severe aGVHD. Each lot of Pregnyl® will be tested for EGF content prior to administration so that the precise EGF dose administered is known.

4 Study Design

This multi-center phase I/II study will use Continual Reassessment Method (CRM) to establish a maximum tolerated dose (MTD) of human chorionic gonadotropin and epidermal growth factor supplementation (hCG) as an adjunct to facilitate improved mucosal healing and immune tolerance in conjunction with accepted, standard immunosuppressive therapy in the setting of high-risk (Arm 1), steroid dependent (Arm 2A), and steroid-refractory (Arm 2B) acute graft-versus-host disease (aGVHD).

Enrollment and dose escalation of Pregnyl® will be independent for each arm.

Arm 1, Phase I: For each arm up to 5 dose levels of Pregnyl® will be tested; however dose levels -1 and -2 will be used only if dose level 1 proves too toxic. In addition to Pregnyl®, patients will continue on their current standard of care aGVHD treatment.

